1.5.1 Preclinical studies

N/A

1.5.2. Clinical studies

N/A

1.6 Risks

1.6.1 Risks of Investigational Product(s)/Intervention(s)

Pneumococcal polysaccharide vaccine is recommended for all adults aged ≥ 65 years and those adults aged 19-64 years with underlying medical conditions that put them at greater risk for serious pneumococcal infection ²⁰. The Advisory Committee on Immunization Practices (ACIP) will continue to review evidence as it becomes available to guide development of a recommendation regarding routine use of PCV13 in adults aged 50 years and older²¹. Eleven immunocompetent subjects between the ages of 25-40 will receive PPV23 without an indication. Safety concerns in this group are not anticipated on the basis of previous safety data generated in young adults vaccinated with pneumococcal vaccines with lower valency (6 and 12) which was used to support the licensure of PPV23^{21a}. Additionally, the safety profile is not expected to differ between young adults without co-morbidities and adults with a medical indication to receive PPV23.

PNEUMOVAX®23, manufactured by Merck (Whitehouse Station, NJ), is indicated for vaccination against pneumococcal disease caused by those pneumococcal types included in the vaccine. The most common adverse experiences reported in >10% of subjects vaccinated with PNEUMOVAX®23 in clinical trials were: local reaction at injection site including pain/soreness/tenderness, erythema, swelling/induration and systemic reaction, mostly with asthenia/fatigue, myalgia and headache.

HIPC: VAX-003

CONFIDENTIAL

Other Adverse reactions identified during post approval use of PNEUMOVAX 23 include: Guillain-Barré syndrome, radiculoneuropathy, seizure, angioneurotic edema, cellulitis, nausea, vomiting, arthralgia, arthritis, limb mobility decreased, paresthesia, weakness, anaphylactoid reaction, lymphadenitis, serum sickness. Because these reactions are reported voluntarily from a population of uncertain size, it is not always possible to reliably estimate their frequency or their causal relationship to product exposure.²².

PREVNAR®13, manufactured by Pfizer (New York, NY), is indicated in adults (50 years or older) for prevention of pneumonia and invasive disease caused by those pneumococcal types included in the vaccine. In adults aged 50 years and older solicited adverse reactions reported in >10% of subjects vaccinated with PREVNAR®13 were: pain at the injection site (>50%), fatigue (>30%), headache (>20%), muscle pain (>20%), joint pain (>10%), decreased appetite (>10%), injection site redness (>10%), injection site swelling (>10%) and limitation of arm movement (>10%)²³. In one randomized study comparing safety of PCV13 to PPV23 in 60-64 years old previously unvaccinated, the frequency of local reactions was not statistically significant in both arms except for pain (more frequent in the PCV13 arm). Also the frequency of systemic reactions was not statistically different in both arms except for decrease in appetite, joint and muscle pains (more frequent in the PPV23 arm)²³. In 6 studies comparing the safety of PCV13 to PPV23, SAE were similar among both groups (around 6% at 6 months post vaccination)^{23.}

Eleven immunocompetent subjects between the ages of 25-40 will receive PCV13 without an indication. The safety profile of PREVNAR13® in immunocompetent healthy adults aged 25-40 years -including both systemic and injection-site adverse events- is not expected to be different than in subjects \geq 50 years old. Safety concerns in this group are not anticipated on the basis of previous safety data generated in young adults vaccinated with pneumococcal conjugate vaccines with lower valency (7). Multiple studies have been published on the use of PREVNAR7® in immunocompromised hosts in transplant recipients^{23a} and HIV infected subjects ^{23b} with acceptable safety profile. In one study with 25 young adults non HIV infected between the ages of 29-46, side effects with PREVNAR7® were mild (98%) mostly involving local tenderness, malaise, and myalgia. These side effects occurred within 7 days after vaccination and none were severe or life-threatening ^{23b}.

CONFIDENTIAL

Revaccination with PPV23 is recommended by the ACIP for subjects with functional or anatomic asplenia and for persons with immunocompromising conditions²⁰, although, this population is not eligible for the current study. However, the ACIP recommends that those who received PPV23 before age 65 years for any indication should receive another dose of the vaccine at age 65 years or later if at least 5 years have passed since their previous dose.

Persons aged ≥ 65 years should be administered a second dose of vaccine if they received the vaccine ≥ 65 years previously and were aged <65 years at the time of primary vaccination. Revaccination with PNEUMOVAX®23 is considered safe although for subjects aged ≥ 65 years the overall injection-site adverse experiences rate was higher following revaccination (79.3%) than following primary vaccination (52.9%). The rate of vaccine-related systemic adverse experiences was also higher following revaccination (33.1%) than following primary vaccination (21.7%) in subjects ≥ 65 years of age²². With revaccination there is a potential risk of hyporesponsiveness with certain serotypes ^{24, 25}. In both of these longitudinal studies, patients were, of course, older at the time of revaccination than at first vaccination and so it is possible that some of the differences in the immune response to revaccination were due to an age-effect, rather than to an effect of prior receipt of pneumococcal polysaccharide vaccine.

Ortqvist et al. also show how the responses in the elderly are serotype specific, with some serotypes eliciting poorer responses than others²⁶. A recent study by Manoff et al., show that both IgG antibodies and functional antibodies persist in persons older than 65 year above baseline concentrations five year after primary vaccination and revaccination²⁷. Although the responses were slightly lower after revaccination there was no blunting of the responses to a second dose of the polysaccharide vaccine. Responses are markedly different in the elderly if the polysaccharide vaccine is given after the conjugate vaccine, where there is clear evidence of the lack of booster response and possible hyporesponsiveness regardless of the dose of conjugate vaccine used for priming ^{28, 29}. In contrast, immunologic hyporesponsiveness is not seen with PCVs, and repeated doses of PCVs can be given to without diminishment of the immune response ^{28, 30}.

However, it should be noted that because the quantity of antibodies that correlate with protection against pneumococcal disease has not been clearly defined, it is unknown if the lower antibody levels seen on revaccination correlate with inferior protection. There is also the added advantage of increased serotype coverage by the PPV23. Currently, there are no

published recommendations from the ACIP regarding the subsequent use of PCV13 in immunocompetent adults previously vaccinated with PCV13.

1.6.2 Risk of Study Procedures

The discomforts of this study include having blood drawn, intramuscular (IM) injection, and possible allergic reactions to the components the pneumococcal vaccines administered in the study.

Drawing blood causes transient discomfort and may cause fainting. Bruising at the blood draw site may occur but can be prevented or lessened by applying pressure to the draw site for several minutes. Intramuscular injection also may cause transient discomfort. The use of aseptic technique will make infection at the site where blood will be drawn or where the vaccination is given extremely unlikely. Vaccines used in the study will be a single vial dose preventing the risk of over or under dosing and the potential risk of contamination when compared to multidose vials.

In the clinical trials of PNEUMOVAX® 23 ^{22,} the most common local adverse events at the site of injection were pain/tenderness/soreness (60.0%), swelling/induration (20.3%), and erythema. The most common systemic adverse experiences were headache (17.6%), asthenia/fatigue (13.2%), and myalgia (11.9%). All of these adverse reactions were reported at a rate lower than 10% after receiving a placebo injection.

In the post-marketing experience of PNEUMOVAX®23, the following additional adverse reactions have been identified: Cellulitis, Malaise, Fever (>102°F), Warmth at the injection site, Decreased limb mobility, Peripheral edema in the injected extremity, Nausea, Vomiting, Lymphadenitis, Lymphadenopathy, Thrombocytopenia in patients with stabilized idiopathic thrombocytopenic purpura, Hemolytic anemia in patients who have had other hematologic disorders, Leukocytosis, Anaphylactoid reactions, Serum Sickness, Angioneurotic edema, Arthralgia, Arthritis, Paresthesia, Radiculoneuropathy, Guillain-Barré syndrome, Febrile convulsion, Rash, Urticaria, Cellulitis-like reactions, and Increased serum C-reactive protein. In the clinical trials of PREVNAR® 13 ²³, the most common solicited local reactions were pain (69-88%), limitation of arm movement (24-41%), swelling (10-22%), and redness (12-20%). The most common systemic adverse experiences were generalized new muscle pain (47-62%), generalized aggravated muscle pain (16-32%), generalized new joint pain (16-32%), generalized aggravated

joint pain (14-26%), decreased appetite (15-25%), chills (20-24%), headache (50-66%), fatigue (51-63%).

1.6.3Risk of Concomitant Medications, Prophylactic Medications and
Rescue MedicationsRescue Medications

We do not anticipate the use of any other medication; however should anaphylactic or hypersensitivity reactions occur, an epinephrine (1:1000) and diphenhydramine injections are readily available at the Hope Clinic during vaccine use. Epinephrine injection can be associated with high blood pressure, arrhythmia, lightheadedness, nervousness, restlessness, tremor, shortness of breath and diaphoresis. The frequency of these side effects is not defined. Diphenhydramine injection can be associated with low blood pressure, arrhythmia, confusion, dizziness, sedation, restlessness, diarrhea, nausea and urinary retention. The frequency of these side effects is also not defined.

Subjects are allowed to use acetaminophen or NSAIDs if they experience a moderate to severe local or systemic side effects after vaccine administration.

1.7 Benefits

1.7.1 Benefits of Investigational Product(s)/Intervention(s)

Participants will have the benefit of receiving a licensed pneumococcal vaccine which may offer protection against pneumococcal disease. Also the knowledge gained from this study could facilitate the design of more effective pneumococcal vaccines for the geriatric population.

1.7.2 Benefits of Study Procedure(s)

None

2. **OBJECTIVES**

PCV13 induces better functional immune responses when compared to PPV23 in older naïve adults. We hypothesize that this is due to intrinsic defects in innate responses that could explain the poor immunogenicity of PPV23 when compared to PCV13. Therefore, we propose to extensively study innate and adaptive immune responses generated after administration of either pneumococcal polysaccharide or conjugate vaccines in older adults.

2.1 **Primary Objective(s)**

To analyze the generic innate immune signatures that correlate with the magnitude of the adaptive immune responses (opsonophagocytosis [OPA] titers) at day 30 in order to identify the correlation signatures of the innate immune responses to PPV23 and PCV13.

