In summary the proposed study offers an unprecedented opportunity to capture the global architecture of immune responses to PPV23 versus PCV13 in the elderly. This is likely to have a major impact in two areas: (i) the elucidation of unique signatures of innate immune response that predict vaccine immunogenicity, and will thus be relevant from a public health perspective; (ii) such unique signatures of innate immune response may illuminate the immunologic defects responsible for sub-optimal immunity in the elderly population when using a polysaccharide vaccine when compared to a conjugate vaccine.

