3.1.3.5. Comparison of generic innate immune responses at days 1, 3 and 7 with adaptive immune responses [Opsonophagocytosis assay OPA titers and ELISA] at years 2-3.5 post vaccination with either PPV23 or PCV13.

Note: This will include - but not only - a comparison of identified innate signature variables and correlation signature variables between elderly (60 to 89 yo) recipients of PCV13 and young (25-40yo) recipients of PPV23.

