5.2 Formulation, Packaging, and Labeling

PNEUMOVAX® 23 (Pneumococcal Vaccine Polyvalent) is a sterile, liquid vaccine for intramuscular or subcutaneous injection. It consists of a mixture of highly purified capsular polysaccharides from the 23 most prevalent or invasive pneumococcal types of *Streptococcus pneumoniae*, including the serotypes that most frequently cause invasive drug-resistant pneumococcal infections among children and adults in the United States.

| 23 Pneumococcal Capsular Types Included in PNEUMOVAX 23 | | |
|--|---|--|
| Nomenclature | Pneumococcal Types | |
| | | |
| Danish | 1 2 3 4 5 6B** 7F 8 9N 9V** 10A 11A 12F 14** 15B 17F 18C 19F** 19A** 20 22F 23F** 33F | |
| ** These serotypes most frequently cause drug-resistant pneumococcal infections ¹ | | |

PNEUMOVAX 23 is manufactured according to methods developed by the Merck Research Laboratories. Each 0.5 mL dose of vaccine contains 25 micrograms of each polysaccharide type in isotonic saline solution containing 0.25% phenol as a preservative.

PNEUMOVAX 23 will be supplied as a single-dose vial of liquid vaccine.

PREVNAR 13®, Pneumococcal 13-valent Conjugate Vaccine (Diphtheria CRM197 Protein) is a sterile suspension of saccharides of the capsular antigens of *Streptococcus pneumonia* serotypes 1, 3, 4, 5, 6A, 6B, 7F, 9V, 14, 18C, 19A, 19F, and 23F, individually linked to nontoxic diphtheria CRM197 protein. Each serotype is grown in soy peptone broth. The individual polysaccharides

are purified through centrifugation, precipitation, ultrafiltration, and column chromatography. The polysaccharides are chemically activated to make saccharides, which are directly conjugated by reductive amination to the protein carrier CRM197, to form the glycoconjugate. The individual glycoconjugates are compounded to formulate Prevnar®13. Potency of the formulated vaccine is determined by quantification of each of the saccharide antigens and by the saccharide to protein ratios in the individual glycoconjugates. Each 0.5 mL dose of the vaccine is formulated to contain approximately 2.2 µg of each of *Streptococcus pneumoniae* serotypes 1, 3, 4, 5, 6A, 7F, 9V, 14, 18C, 19A, 19F, 23F saccharides, 4.4 µg of 6B saccharides, 34 µg CRM197 carrier protein, 100 µg polysorbate 80, 295 µg succinate buffer and 125 µg aluminum as aluminum phosphate adjuvant.

Note: No additional labeling of the vaccines will be required

5.3 **Preparation, Administration, and Dosage**

PNEUMOVAX®23:

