7. STUDY VISITS AND PROCEDURES

7.1 Enrollment and Randomization

This research study will be explained in lay terms to each potential research participant. The potential participant will sign an informed consent form before undergoing any study procedures. Participants who are deemed eligible for the study (see sections 4.1 and 4.2) will be enrolled and assigned a unique participant number. Approximately eighteen months are needed for enrollment. The duration of participation for each subject is approximately 6 months. An additional optional blood draw will be offered 2-3.5 years after enrollment.

Eighty eight subjects (22 subjects (ages 25-40) and 66 subjects (ages 60-89)) will be randomized to receive PPV23 or PCV13 in a 1:1 ratio.

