9. SAMPLE SIZE CALCULATIONS AND STATISTICAL PLAN

9.1. Sample Size and Power Calculations

The study is explorative. Not enough preliminary data exists to support accurate calculation of the sample size. However we conducted a sample size analysis based on hypothetical scenarios and knowledge of similar studies. Based on previous studies performed at the Hope Clinic and the Vaccine Research Trials Center, the rate of subjects that become ineligible during the study (i.e. do not meet exclusion/inclusion criteria anymore, lost to follow-ups, unable to have blood draws) is between 5 to 10%. Assuming 10% attrition rate, 88 subjects will be recruited and 1:1 randomized into the two treatment groups, resulting in an expected 80 subjects for data analysis. The sample size is on-par with similar studies. In the case that the sample size of subjects missing any of the 4 draws required for the primary endpoint [meaning draws at days 1, 3, 7(\pm 1), and 30 (\pm 7)] is higher than 10% of the 88 subjects to be recruited for the study, we will recruit extra patients to maintain the target sample size of 80 subjects.

The randomization process will be detailed in the MOP. At the center of this study is the identification of generic innate signatures and finding their correlations with the adaptive immune response. The generic innate signatures will be identified from both traditional immune parameters measured by FACS/Luminex assays and array-based gene expression will be measured by microarray experiments. The generic innate signatures will be identified for different treatment groups separately. The traditional immune parameters and array-based gene expression that change after immunization are considered generic innate signatures. The traditional immune parameters and array-based gene expression that change after immunization are considered generic innate signatures. The traditional immune parameters and array-based gene expression that are correlated with the adaptive immune responses (day 30 OPA titers, day 30 IgG levels, day 180 serotype specific avidity indexes, plasmablasts also) are considered correlation signatures of the innate immune responses.

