After identifying the innate immune signatures and correlation immune signatures within each elderly treatment group and each young treatment group, there is an interest in comparing the signatures between PPV23 and PCV13 recipients. Here we consider four groups: elderly PPV23, elderly PCV13, young PPV23 and young PCV13. Each group has two signatures – innate signature and correlation signature. For each group, the correlations signature is a subset of the innate signature. For both the innate and the correlation signature, we will make comparisons between:

A-- the two vaccine groups in the same age category: elderly (60-89) receiving PPV23 v.s. elderly (60-89) receiving PCV13 and young (25-40) receiving PPV23 v.s. young (25-40) receiving PCV13),

B-- all the other possible combinations: elderly (60-89) receiving PPV23 v.s. young (25-40)
receiving PPV23; elderly (60-89) receiving PPV23 v.s. young (25-40) receiving PCV13; elderly (60-89) receiving PCV13 v.s. young (25-40) receiving PPV23; elderly (60-89) receiving PCV13
v.s. young (25-40) receiving PCV13.

This part of the analysis will depend on the results of the aforementioned analysis and hard to specify at this stage.

As a preliminary consideration, the identified innate signature variables and correlation signature variables can be contrasted between groups using descriptive statistics, such tabulation and Venn diagrams.

5. Comparison of generic innate immune responses at days 1, 3 and 7 with adaptive immune responses [Opsonophagocytosis assay OPA titers and ELISA] at years 2-3.5 post vaccination with either PPV23 or PCV13.

For correlation analysis, the analysis is similar to primary endpoint 3. Instead of using all the data, we will analyze data in the elderly.

Enriched biological pathways can be identified using each type of signature in each of the four groups considered above (i.e. elderly (60-89) receiving PPV23, elderly (60-89) receiving PCV13, young (25-40) receiving PPV23 and young (25-40) receiving PCV13), using gene ontology (computer program that generates biological networks from gene lists). Then the enriched pathways can be manually compared between the different treatment groups as per #A and #B above. Biological interpretations of the differences will be made.

9.2.2. Patient populations

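### The elderly PPV23–PCV13 signature difference is a whole-product effect, and exploratory endpoint 4 compares age groups by lists of unequal power without forming the age-by-vaccine contrast

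*Combined protocol and SAP*

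**What the plan says.** - **Hypothesis.** Section 2, after stating that PCV13 gives better functional responses in older naïve adults, says: "We hypothesize that this is due to intrinsic defects in innate responses that could explain the poor immunogenicity of PPV23 when compared to PCV13". Section 1.1 adds that innate signatures "may illuminate the immunologic defects responsible for sub-optimal immunity in the elderly population when using a polysaccharide vaccine when compared to a conjugate vaccine". The plan does not define what makes a defect intrinsic.
- **Allocation.** Section 7.1: "Eighty eight subjects (22 subjects (ages 25-40) and 66 subjects (ages 60-89)) will be randomized to receive PPV23 or PCV13 in a 1:1 ratio".
- **Products.** Section 5.2 says of PPV23: "Each 0.5 mL dose of vaccine contains 25 micrograms of each polysaccharide type in isotonic saline solution containing 0.25% phenol as a preservative"; no carrier or adjuvant is listed. For PCV13 it gives about 2.2 µg of each of 12 saccharides and 4.4 µg of 6B, linked to CRM197 (34 µg), with 125 µg "aluminum as aluminum phosphate adjuvant".
- **Comparison singled out.** The Note under 3.1.3.5, also in the synopsis, picks out "correlation signature variables between elderly (60 to 89 yo) recipients of PCV13 and young (25-40yo) recipients of PPV23" while saying that other comparisons are included too.
- **Comparisons planned.** Section 9.2.1, exploratory endpoint 4, lists the two same-age vaccine pairs, the two same-vaccine age pairs and the two crossed pairs, one being "elderly (60-89) receiving PCV13 v.s. young (25-40) receiving PPV23". The stated tools are tabulation and Venn diagrams. Under exploratory endpoint 5, pathways enriched in each signature are then compared by hand across the same pairs.

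**The concern.** Two questions are easily run together. One is whether the two products trigger different innate responses in older adults. The other is whether older adults have an innate deficit that matters more with a polysaccharide vaccine. The randomised elderly comparison answers only the first: an aluminium, carrier or dose signature could separate the arms with no host defect at all.

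The second question needs the young groups, and needs the age gap under PPV23 set against the age gap under PCV13. The plan has all four groups but makes no such estimate. What it does compare, lists of features passing a threshold, depends strongly on group size. At stake is how the mechanistic hypothesis is reported.

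**Working it through.** **1. Product differences (section 5.2).**
- Per shared serotype: 25 / 2.2 = 11.4-fold; for 6B, 25 / 4.4 = 5.7-fold.
- Total saccharide: 23 × 25 = 575 µg against 12 × 2.2 + 4.4 = 30.8 µg; 575 / 30.8 = 18.7-fold.
- Twelve serotypes are shared, 6A is in PCV13 only, and 23 − 12 = 11 are in PPV23 only.

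**2. What each pair estimates.** Write a group's mean change from Day 0 as μ + a (if elderly) + v (if PPV23) + g (if both). An age deficit specific to the polysaccharide vaccine is g.

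| Comparison | Estimates |
|---|---|
| Elderly PPV23 − elderly PCV13 | v + g |
| Young PPV23 − young PCV13 | v |
| Elderly − young, PPV23 | a + g |
| Elderly − young, PCV13 | a |
| Elderly PCV13 − young PPV23 (the Note) | a − v |
| Elderly PPV23 − young PCV13 | a + v + g |

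The elderly pair cannot separate v from g, and the Note's pair cannot separate a from v, at any sample size. The third row minus the fourth gives g. The plan lists these components but never takes their difference.

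**3. Group sizes.** 66 / 2 = 33 and 22 / 2 = 11 per arm. With 10% attrition these become 33 × 0.9 = 29.7 and 11 × 0.9 = 9.9, so about 30 and 10. Section 9.1 agrees: "Assuming 10% attrition rate, 88 subjects will be recruited and 1:1 randomized into the two treatment groups, resulting in an expected 80 subjects".

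**4. The plan's power, reproduced.** Two-sided paired t-test, noncentrality d√n, n = 30, 29 df:
- d = 0.66, alpha 0.01: 0.66 × √30 = 3.61, power 79.7% (stated 80%).
- d = 0.88, alpha 0.0005: 0.88 × √30 = 4.82, power 79.8% (stated 80%).

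**5. Same settings in a young arm (n = 10, 9 df).**
- d = 0.66, alpha 0.01: 0.66 × √10 = 2.09, power 19.6%.
- d = 0.88, alpha 0.0005: 0.88 × √10 = 2.78, power 6.5%.

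Take a feature with the same true change in both age groups. The groups are independent, so the chance that it is listed for the elderly only is 0.797 × (1 − 0.196) = 0.64 for an immune parameter and 0.798 × (1 − 0.065) = 0.75 for a gene. A Venn diagram would show most of these shared changes as elderly-specific.

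**6. Precision of the missing contrasts.** In SD units of the change score, assuming equal SDs:
- Same-vaccine age gap: SE = √(1/30 + 1/10) = 0.365; 95% interval ± 1.96 × 0.365 = ± 0.72.
- Difference of the two gaps: SE = √(2 × (1/30 + 1/10)) = 0.516; 95% interval ± 1.96 × 0.516 = ± 1.01.

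| | Alpha 0.05 | 0.01 | 0.0005 |
|---|---|---|---|
| Age gap detectable with 80% power (SD) | 1.05 | 1.31 | 1.72 |
| Difference of gaps detectable with 80% power (SD) | 1.47 | 1.81 | 2.33 |

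At the plan's planning pairs (0.66 SD with alpha 0.01; 0.88 SD with alpha 0.0005), power is 20% and 10% for one age gap, and 9% and 3% for the difference of gaps.

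**The case against.** Several points on the other side stand, and they limit the finding.

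- **Misattribution is not planned.** A reader might infer that the plan will report a formulation effect as a host defect. The documents do not say so. The hypothesis and section 1.1 are both hedged, and section 9.2.1 calls this analysis hard to specify in advance and promises only biological interpretation.
- **The crossed pair is not the only age comparison.** That too might be inferred from the Note, but the Note is expressly non-exclusive and section 9.2.1 lists both same-vaccine age pairs.
- **The primary analyses are not affected.** Signatures, and their correlation with day 30 OPA titers, are assessed within each elderly arm, where formulation is constant. The between-vaccine signature comparison is exploratory.
- **The term is open.** Section 1.5 discusses PPV23's own TLR signalling and cytokine profile. If the defect means weak triggering by PPV23, the randomised elderly contrast does address it, as a whole-product effect. Section 1.1 leans towards a host reading, so the text is ambiguous rather than wrong.
- **The alternative is imprecise and not fully clean.** Age is a stratum, not a randomised factor. An interaction depends on the scale, and floor effects can produce one. The pathway score has still to be defined, and many pathways bring multiplicity.
- **The small young groups are disclosed.** Section 9.2.1 says that they lack power for reliable signatures, confines them to exploratory endpoints and relies on pathways.

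The last point does not rescue list comparison. The pathways are derived from each group's signature, so they inherit its unequal power. Section 9.4 permits alternative methods, including gene set enrichment, but does not name the contrast.

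**Conclusion.** The point holds as a limit on interpretation and a correctable weakness in exploratory endpoint 4. The elderly between-vaccine signature difference is a whole-product effect. The planned age comparisons rest on lists whose overlap is driven partly by group size (about 80% against 20% or 6% power for the same true change), and the age-by-vaccine contrast is missing.

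The list-power figures use the planning settings of section 9.1. The actual selection rules (p ≤ 0.01 with average fold change ≥ 3; FDR ≤ 0.1) will give other percentages, but the imbalance between 30 and 10 subjects remains. The interval of about ±1.0 SD assumes equal SDs and 30, 30, 10 and 10 evaluable subjects.

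No stated figure is wrong, and no primary or secondary result changes. Requiring the crossed pairs to be deleted, or barring any statement about a defect until the interaction is established, would go further than the documents justify.

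**What to change.** 1. In section 9.2.1, exploratory endpoint 4, for change from Day 0 in each immune parameter and in a pathway score defined beforehand, estimate (i) elderly minus young within PPV23, (ii) the same within PCV13, and (iii) the difference (i) − (ii), each with a confidence interval. Keep the tables and Venn diagrams as description.
2. Amend the Note under 3.1.3.5 and in the synopsis to single out these contrasts; keep any crossed pairs as descriptive only.
3. State in section 2 or 9.2.1 that signature differences between the elderly arms are whole-product effects, and say what an intrinsic defect means.

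The cost is protocol wording and a few contrasts. Section 7.3 and section 7.4 already schedule the Day 0, 1, 3 and 7 draws for all participants. The drawback is precision: contrast (iii) has an SE of about 0.52 SD, age is not randomised, and the question will often have to be reported as unresolved.
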